5.0 INCLUSION AND EXCLUSION CRITERIA/STUDY POPULATION

5.1 Initial Screening Methodology

Initial screening eligibility will be conducted by the PI or trained research personnel. Subjects with a self-reported history of depression and opioid misuse or illicit opioid use for which they report being abstinent for at least 3 months (early remission) will be eligible to complete informed consent and baseline evaluation.

5.2 Inclusion Criteria

A subject may be eligible for enrollment if all the following inclusion criteria apply within the thirty days prior to first experimental session:

1. Between the ages of 18 to 64 years old.
2. Able to provide informed consent.
3. Meet DSM-5 criteria for Major Depressive Disorder, without psychotic features based on clinical interview.
4. Score at least 20 on the Montgomery-Asberg Depression Rating Scale (MADRS, moderate or severe depression).
5. Must meet criteria for opioid use disorder in early or sustained remission (3 months or great) by DSM-5 based on clinical interview.
6. Subjects taking other psychotropic medications (e.g. anti-depressants, anxiolytics, methadone, buprenorphine, naltrexone) must be maintained on a stable dose for at least four weeks before study initiation.

5.3 Exclusion Criteria

Subjects will be excluded from the study if any of the following criteria apply:

1. They are considered an immediate suicide risk by clinician assessment, self-report a suicide attempt within the past year or felt to be likely to require hospitalization during the study.
2. Subjects who meet DSM-5 criteria for current bipolar disorder based on clinical interview.
3. Subjects who meet DSM-5 criteria for current or history of psychotic spectrum disorders based on clinical interview.
4. Subjects meeting DSM-5 criteria for current substance use disorder (*i.e.*, not in early or sustained remission) other than tobacco use disorder.
5. Subjects who report use of ketamine >20 times in the past or who meet DSM-5 criteria for Other Hallucinogen Use Disorder due to ketamine use including subjects who are currently in early or sustained remission.
6. Women who are pregnant or nursing, and women who do not consent to use methods of highly effective birth control during the interventional phase of the study.
7. Subjects with hypertension as defined by a baseline visit systolic blood pressure (SBP) >140 mmHg or a diastolic blood pressure (DBP) >90 mmHg.
8. A history of allergic or other adverse reaction to ketamine (or its excipients).
9. Clinically significant physical exam findings or self-reported medical conditions for which a transient increase in blood pressure could be significantly detrimental (e.g. glaucoma, aneurysmal disease, cardiovascular disease, or end-stage renal disease).
10. QTc will be measured in subjects currently taking methadone and those with QTc 450ms or longer will be excluded.
11. Subjects who live greater than 20 miles from the study site and cannot arrange their own transportation will be excluded from the study.
12. Subjects with clinically significant kidney or liver impairment.

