7.3 Schedule of Assessments

The instruments to be used are standardized, have good psychometric properties, and are widely used. The schedule of study assessments is provided in **Table 1**.

Table 1: Schedule of Assessments

Instrument Name	Purpose	TIME POINT		
		BL (Wk 0)	Tx 1-8 (Wk 1-8)	Follow-up (Wk 9, 10, 12, 16)
Self-Reports and Consents				
Informed Consent	Obtain informed consent	X		
Demographics Form	Sample characterization	X		
Beck Depression Inventory-II	Self-reported assessment of depression symptom severity	X	X	X
Visual Analog Scale (VAS)	Measure subjective levels of opioid craving	X	X	X
General Anxiety Disorder (GAD-7)	Self-report of anxiety symptom severity	X	X	X
Mystical Experiences Questionnaire (MEQ)	Measure of perceptual experiences		X	
Brief Pain Inventory	Measure of pain and quality of life	X	X	X
Insomnia Severity Index (ISI)	Assess insomnia and sleep quality	X	X	X
Five Facets of Mindfulness (FFMQ)	Assess aspects of mindfulness related	X	X	X
PTSD Checklist (PCL-5)	Measure of PTSD symptoms	X	X	X
Fagerstrom Test of Nicotine Dependence (FTND)	Measure of nicotine dependence	X	X	X
Timeline Follow-Back (TLFB)	Measure of substance use	X	X	X
Clinician Assessments				
History and Physical Exam	Eligibility assessment	X		
Vital Signs Measurement	Obtain readings of blood pressure, pulse, temperature, respirations and pulse oximetry	X	X*	
Montgomery-Asberg Depression Rating Scale (MADRS)	Primary Outcome: Clinician assessed measure of depression symptom severity	X	X	X
Pre-screening Questionnaire	To assess for basic eligibility criteria before completing a full baseline visit.	X		
Laboratory and Procedural Tests				
Urine Pregnancy Test (female subjects only)	Eligibility assessment	X	X	
Urine Drug Screen	Assessment of illicit drug use	X	X	
Electrocardiogram (ECG; subjects on methadone only)	Assessment of cardiac function	X		

* Vital signs (blood pressure, pulse, respiratory rate, and pulse oximetry) will be obtained prior to treatment sessions and at 60 minutes post-treatment. Temperature will be monitored immediately prior to treatment. If there is an increase in systolic or diastolic blood pressure >30 mm Hg from baseline, or an increase in pulse rate >30 bpm from baseline, subjects will be treated with standard of care antihypertensive medications (i.e. clonidine) and the measurements will be repeated every 20 minutes until BP and pulse are within 30 points of the baseline values.

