7.4 Baseline Assessment Procedures

After completing study informed consent, participants will undergo a comprehensive evaluation to assess for inclusion and exclusion criteria. This will include self-reports and clinician assessments as shown in Table 1. This will also include assessment of depression severity and participants at highest risk for suicidality based on clinician assessment, those with a self-reported suicide attempt within the past year, and those felt likely to require hospitalization during the course of the study will be excluded. The comprehensive exam will also include a history and physical exam by the study PI (pulse oximetry measurements will be a component of the respiratory evaluation) and baseline medication evaluation for potential harmful interactions. Urine pregnancy tests will be completed for every woman of childbearing potential. Urine drug screening will be collected at baseline and prior to each ketamine session to monitor

for opioid and other illicit substance use. For patients currently taking methadone, ECG will be performed to assess for cardiac function with QTc interval of 450ms or longer being exclusionary. Assessments may be conducted by telehealth with vital signs to be provided by participant's home or pharmacy measurement.

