7.5 Intervention Visit Procedures

Prior to administration of the study compounds, participants will complete self-report questionnaires and clinical assessments. The study physician will disinfect the subject's shoulder using an alcohol wipe, and the study physician will then administer the medication by intramuscular administration into the participant's deltoid muscle. Vital signs will be monitored prior to treatment, and at 60 minutes post-treatment. If during the post-administration observation period, ketamine administration causes an increase in systolic or diastolic blood pressure >30 mm Hg from baseline, or an increase in pulse rate >30 bpm from baseline, the subject will be treated with standard of care antihypertensives (i.e. clonidine), and repeat vital sign measurements will be taken approximately every 20 minutes until blood pressure and pulse are within 30 points of baseline values. Standard of care antihypertensive medications will be procured via intrainstitutional transfer from MUSC investigational drug services pharmacy distribution center. They will be stored in a DHEC compliant locked box within a locked room accessible only to study team members. If the subject experiences symptoms of hypertensive emergency, the subject will not receive further administration of ketamine and will be withdrawn from the study. After completion of the injection, participants until returned to baseline per clinical assessment which time they will undergo debriefing and complete assessments of their perceptual experience of the intervention. We will evaluate the effects of a weekly interventions for 8 sessions. Participants will return for follow-up assessment 1, 2, 4 and 8 weeks following final medication session. Follow-up visits may be conducted by telehealth.

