
Pre-Intervention Assessment: A comprehensive exam will be conducted as part of the baseline assessment to minimize risks from study participation. This will include assessment of depression severity, and participants at highest risk for suicidality will be excluded. The comprehensive exam will also include a history and physical exam by the study PI (pulse oximetry measurements will be a component of the respiratory evaluation), baseline medication evaluation for potential harmful interactions, and electrocardiogram to ensure safe study participation.

Peri-Intervention Monitoring: Subjects will be continuously medically and psychiatrically monitored throughout the course of the intervention and until return to medical and psychiatric baseline. Subjects will be instructed not to eat for at least 2 hours before taking the intervention sessions to reduce the risk of nausea and vomiting. Emergency services will be contacted in the event of any medical complications. Subjects will not be allowed to drive themselves after the interventional visits, and alternative transportation will be arranged if needed.

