11.2 Physical Risks

The most significant physical adverse event from ketamine is a transient increase in blood pressure, which in previous studies was experienced by 29.8% of subjects with a mean systolic blood pressure increase of 19.6 mmHg +/- 12.8 mmHg and a mean diastolic blood pressure increase of 13.4 mmHg +/- 9.8 mmHg. Peak levels are reached on average 40 minutes post-treatment and resolve by 240 minutes post-treatment (Wan et al., 2015). Participants experiencing clinically significant hypertension (greater than 180 mmHg SBP or greater than 105 mmHg DBP, or greater than 30 mmHg SBP or DBP from baseline values) will be treated with standard of care hypertensives (e.g. clonidine) and monitored until symptom resolution.

The most prevalent physical adverse effect was transient sedation and occurs in approximately 16% of patients receiving ketamine. Sedation will be monitored via continuous clinical observation during interventional sessions. A medical emergency team will be called for participants that are unable to be aroused with painful trapezius squeeze or that experience hypoxia (i.e. a pulse oximeter reading of 92% or less), although in the investigative team's extensive experience using ketamine clinically for depression at these doses, such serious events have never occurred. Vital signs will be routinely monitored during treatment and emergency airway equipment will be immediately available. Subjects will be monitored for 2 hours post-dose by trained healthcare professionals (eg PI, co-I, or study nurse). Due to transient cognitive impairment associated with sedation, participants will not be allowed to drive themselves following the interventions. Subjects who do not have transportation and live within 20 miles will receive compensation for taxi, Uber or Lyft transportation to and from medication sessions up to \$100 each way. Subjects who live greater than 20 miles from the study site and cannot arrange their own transportation will be excluded from the study. Participants will be advised not to operate heavy machinery for at least 24 hours after the interventions.

There are also the standard risks associated with intramuscular injections including temporary local pain, irritation, or redness at the site of the injection. There is a very small (<1%) risk of infection, muscle fibrosis, or persistent muscle or nerve damage at the site of injection.

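### No written rule withholds or delays ketamine for a high pre-dose blood pressure; the 140/90 mmHg limit applies only at the baseline visit

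*Combined protocol and SAP*

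**What the plan says.** Section 5.3, exclusion 7, keeps out "Subjects with hypertension as defined by a baseline visit systolic blood pressure (SBP) >140 mmHg or a diastolic blood pressure (DBP) >90 mmHg". Section 7.4 allows the baseline work to be remote: "Assessments may be conducted by telehealth with vital signs to be provided by participant's home or pharmacy measurement".

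In section 7.3, Table 1 places the baseline visit at week 0 and the ketamine sessions at weeks 1 to 8. Its footnote says that blood pressure and other vital signs "will be obtained prior to treatment sessions and at 60 minutes post-treatment".

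Three actions depend on blood pressure:

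- Section 7.5: "If during the post-administration observation period, ketamine administration causes an increase in systolic or diastolic blood pressure >30 mm Hg from baseline", or if pulse rises by more than 30 bpm, the participant receives an antihypertensive and readings are repeated about every 20 minutes. The Table 1 footnote has the same rule without the words that confine it to the period after dosing.
- Section 11.2: hypertension is clinically significant at "greater than 180 mmHg SBP or greater than 105 mmHg DBP, or greater than 30 mmHg SBP or DBP from baseline values". The action is treatment and monitoring. The 180/105 level does not appear in section 7.5.
- Section 7.5: "If the subject experiences symptoms of hypertensive emergency, the subject will not receive further administration of ketamine and will be withdrawn from the study".

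On general supervision, section 9.0 states: "Subjects will be continuously medically and psychiatrically monitored throughout the course of the intervention", and this continues until the participant is back to baseline.

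**The concern.** Section 11.2 names the transient blood pressure rise as the most significant physical adverse event of ketamine, and exclusions 7 and 9 exist to keep people vulnerable to it from being dosed. The protocol re-measures pressure before each dose but attaches no dosing consequence to the result. Section 7.5 as written therefore permits dosing at a pressure that would have barred entry. The written numeric rules treat a high pressure; none stops ketamine being given on top of one.

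Pregnancy is handled differently. It is also an exclusion, it is re-tested at the treatment visits with eligibility as the stated purpose (Table 1), and section 9.0 makes it a ground for withdrawal. Dose may also step up by 0.25 mg/kg per session on tolerability (section 3.3), with no blood pressure criterion.

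**Working it through.** The protocol gives no figure to reproduce here. The check sets the rules side by side, tests them on one case, and adds an illustration of scale.

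**1. Where the entry limit applies.** The check is made at week 0. It is 1 − 0 = 1 week old at session 1 and 8 − 0 = 8 weeks old at session 8. Only the eligibility check ages; pressure itself is measured again before every session.

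**2. What each rule does.**

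| Rule | Trigger | Action | Pre-dose hold? |
|---|---|---|---|
| 5.3, exclusion 7 | >140 or >90 at baseline visit | Exclude | No |
| 7.5 and Table 1 footnote | Rise >30 from baseline | Treat, re-measure | No |
| 11.2 | >180 or >105, or rise >30 | Treat, monitor | No |
| 7.5 | Symptoms of hypertensive emergency | Stop ketamine, withdraw | No; depends on symptoms |

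**3. Test case (chosen values).** Baseline is 138/88 and the pre-dose reading is 165/100.

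- Against exclusion 7: 138 and 88 are within 140/90, so the participant enters.
- Rise: 165 − 138 = 27 and 100 − 88 = 12. Neither exceeds 30.
- Level: 165 < 180 and 100 < 105.
- Against the entry limit: 165 − 140 = 25 and 100 − 90 = 10 mmHg above it.

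No rule acts, even if the 30 mmHg and 180/105 rules are read as covering the pre-dose reading.

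**4. The undefined baseline.** In the 30 mmHg rule, baseline could mean the baseline visit or the same-day reading. In the test case, section 7.5's trigger is above 138 + 30 = 168 systolic or 88 + 30 = 118 diastolic on the first meaning. On the second it is above 165 + 30 = 195 or 100 + 30 = 130. On the same-day meaning, a high pre-dose reading raises the treatment trigger. Only section 11.2's 180/105 caps it, and section 7.5 does not state that level.

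**5. Scale, as illustration only.** Section 11.2 gives mean rises of 19.6 ± 12.8 systolic and 13.4 ± 9.8 diastolic. Assume that the ± values are standard deviations, that rises are normal, and that they do not depend on the starting pressure. Then:

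P(SBP > 180) = 1 − Φ((180 − pre − 19.6)/12.8)

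- From 140: 20.4/12.8 = 1.59, giving 5.5%
- From 150: 10.4/12.8 = 0.81, giving 20.8%
- From 160: 0.4/12.8 = 0.03, giving 48.8%

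P(DBP > 105) = 1 − Φ((105 − pre − 13.4)/9.8)

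- From 90: 1.6/9.8 = 0.16, giving 43.5%
- From 100: −8.4/9.8 = −0.86, giving 80.4%

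Section 11.2 does not make clear whether the means describe all subjects or only the 29.8% with a rise. If only those, and nobody else crosses the limit, multiply by 0.298. From 140 and 160 systolic the figures become 1.6% and 14.5%; from 90 and 100 diastolic they become 13.0% and 24.0%. On either reading the chance of reaching the protocol's own treatment level climbs with the pre-dose value. The point rests on the text, not on these figures.

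**The case against.** The strongest reply is that dosing is supervised closely. A study physician gives each injection after assessments and vital signs (7.5). The dose starts at 0.5 mg/kg and is capped at 60 mg a day (3.3). Exclusion 9 removes people for whom a transient rise would be dangerous. Monitoring is continuous (9.0), and observation lasts two hours with airway equipment at hand (11.2). Staff must alert the investigator if a participant seems medically compromised (9.0), and the investigator may withdraw anyone at risk (10.0). All of this stands and lowers the risk. None of it gives a value at which the dose is held.

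The test case was also picked to fall between the rules. For someone at 120/75 at baseline, 165/100 is a 45 mmHg systolic rise. The Table 1 footnote, read generously, would then call for treatment and repeat readings. That is fair, but the footnote still does not say that ketamine waits.

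Finally, 140/90 defines hypertension at entry and is not written as a dosing-day limit. A reader might infer that dosing above it breaches the protocol; the documents do not support that. The right hold value is a clinical choice, and the case at 165/100 does not prove that a reading of 142/88 should stop a session.

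**Conclusion.** The gap is real. Vital signs are taken before all eight sessions and no written rule withholds or delays ketamine for a high pre-dose blood pressure. It is a participant-safety point that should be fixed. Nothing in it bears on the definition of the primary outcome, the MADRS.

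Its size is limited in two ways. The protocol gives no distribution of pre-dose readings, so the share of sessions affected is unknown. The illustrative probabilities depend on assumed pre-dose values and a normal model.

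Two stronger inferences should be resisted:

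- A reader might count 10 × 8 = 80 planned doses as doses at risk. That number is exposure, not risk: pressure is measured before each dose and most readings may be unremarkable.
- A reader might add that the 60-minute reading misses the average 40-minute peak given in section 11.2. That concerns monitoring after the dose. The 40-minute figure comes from intravenous experience, and sections 9.0 and 11.2 describe continuous observation and vital signs during treatment. It does not bear on a pre-dose hold.

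**What to change.** Amend three places.

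- **Section 7.5 and the Table 1 footnote, hold rule:** if the pre-dose reading is above 140 systolic or 90 diastolic, repeat it after rest. If it is still above, give no ketamine that day, then reschedule the session or record it as held, with the reading. Use 140/90 as the default because it is the protocol's own entry limit. If the investigator prefers another value, it should be below 180/105 and written down with the reason.
- **Section 7.5 and the Table 1 footnote, treatment rule:** define baseline in the 30 mmHg rule as the same-day, staff-measured pre-dose reading. State section 11.2's 180/105 level beside it in 7.5, so that a high pre-dose reading cannot push the treatment trigger up without limit.
- **Section 5.3:** if baseline vital signs were a home or pharmacy measurement, confirm exclusion 7 on the staff-measured reading before session 1.

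No new measurement is needed. The cost is a short amendment, a few delayed or missed sessions, and possibly a participant excluded at session 1. As an assumption only, if 2% to 10% of pre-dose readings stayed above 140/90 on repeat, 80 × 0.02 = 1.6 to 80 × 0.10 = 8 of the planned sessions would be held or moved.

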5.4 NUMBER OF SUBJECTS

Approximately 10 subjects are planned for enrollment in this study with no gender, race, or ethnicity exclusions.

5.5 SETTING

All procedures will be conducted in private research study rooms on MUSC campus.

5.6 RECRUITMENT METHODS

Recruitment will be conducted through online (*i.e.* Craigslist) and flyer advertisements throughout the hospital and outpatient clinics at MUSC and other local clinics providing OUD treatment.

Initial screening eligibility will be conducted by the PI or trained research personnel. Subjects with a self-reported history of depression and opioid misuse or illicit opioid use for which they report being abstinent for at least 3 months (early remission) will be eligible to complete informed consent and baseline evaluation.

6.0 CONSENT PROCESS

6.1 Qualifications of Study Personnel Obtaining Informed Consent and Capacity of Participants

The research team have completed (or will complete upon hiring) the Miami Collaborative IRB Training Initiative (CITI) course and its associated tests in research ethics. Only the PIs or Co-I's will obtain informed consent.

6.2 Location of Informed Consent

Informed consent will be obtained at the study research offices, in a private and interruption-free environment.

6.3 Method of Obtaining Consent

Study personnel will ensure that the participant is given full and adequate written and verbal information about the nature, purpose, possible risks and benefits of the study. There will be no mandatory waiting period prior to obtaining informed consent, however participants will not be required to make a decision at the time of initial contact. Participants will also be allowed to discuss the study with family or other individuals prior to giving their informed consent. After participants have reviewed the informed consent document, participants will be asked to relay their understanding of key elements related to the study procedures (i.e. voluntary nature of participation, basic study visit procedures, duration of study, anticipated risks and benefits) to ensure their understanding of the study prior to obtaining informed consent. Consent content will be reviewed as necessary to ensure that subjects have an adequate understanding to provide initial and ongoing consent. The participant's signed and dated informed consent will be obtained before conducting any study tests or procedures that are not related to their routine care. The Investigator will maintain the original, signed informed consent document. A copy of the signed informed consent document will be given to the participant.

